7.1 Analysis Endpoints

7.1.1 Primary Efficacy Endpoints (Part A)

The primary efficacy endpoint of Part A is the change from baseline in the rater-administered MADRS total score at Week 6.

7.1.2 Secondary Efficacy Endpoints (Part A)

7.1.2.1 Key Secondary Efficacy Endpoint (Part A)

The key secondary objective of Part A of this study is to compare the efficacy of 2 doses of ITI-007 administered orally once daily to that of placebo in time to first response, defined as the number of days from first dose of study drug to the earliest date the patient experiences a sustained $\geq 50\%$ reduction from baseline in the rater-administered MADRS total score.

7.1.2.2 Other Secondary Efficacy Endpoints (Part A)

- MADRS:
 - Time course of improvement, as measured by mean change from baseline in the MADRS total score at each assessment time point;
 - The proportion of treatment responders, where response is defined as a $\geq 50\%$ decrease in the MADRS total score from baseline at Weeks 1, 2, 3, 4, 5, and 6. Patients who discontinue treatment early will be imputed as non-responders in the responder analysis.
 - The proportion of remitters, where remission is defined as a MADRS total score ≤ 12 at Weeks 1, 2, 3, 4, 5, and 6. Patients who discontinue treatment early will be imputed as non-remitters in the remitter analysis.
 - Change from baseline in MADRS Item 4 “reduced sleep” score for patients with baseline MADRS Item 4 score ≥ 4 (patients with mild sleep disturbance) at Weeks 1, 2, 3, 4, 5, and 6.
 - Change from baseline in MADRS individual item scores at Weeks 1, 2, 3, 4, 5, and 6.
- CGI-BP:
 - Change from baseline in the CGI-BP-S score at Weeks 1, 2, 3, 4, 5, and 6;
- SDS:
 - Change from baseline in the score for each item and total score at Weeks 3 and 6;
- Q-LES-Q-SF:
 - Change from baseline in the percent score at Weeks 3 and 6.

- WHO-5 Well-Being Index
 - Change from baseline in the percent score at Weeks 3 and 6.
- NEO-FFI
 - Change from baseline in the percent score at Week 6.

■ [REDACTED]

■ [REDACTED]
[REDACTED]
[REDACTED]

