The primary objective of Part A of this study is to compare the efficacy of 2 doses of ITI-007 administered orally once daily to that of placebo in mean change from baseline in the total score on the rater-administered Montgomery-Åsberg Depression Rating Scale (MADRS) in patients with bipolar depression at Week 6.

Secondary Objectives

Key Secondary Objective

The key secondary objective of Part A of this study is to compare the efficacy of 2 doses of ITI-007 administered orally once daily to that of placebo in time to first response, defined as the number of days from first dose of study drug to the earliest date the patient experiences a sustained $\geq 50\%$ reduction from baseline in the rater-administered MADRS total score.

Other Efficacy Secondary Objectives of Part A of this study are to compare the efficacy of 2 doses of ITI-007 administered orally once daily to that of placebo in relation to:

- MADRS:
 - Time course of improvement, as measured by mean change from baseline in the MADRS total score at each assessment time point;
 - Time course of improvement, as measured by the proportion of treatment responders where response is defined as a $\geq 50\%$ decrease in the MADRS total score from baseline at each assessment time point, including at Week 6;
 - Time course of improvement, as measured by the proportion of remitters where remission is defined as a MADRS total score ≤ 12 at each assessment time point, including at Week 6;
 - The improvement in sleep, as measured by Item 4 (reduced sleep) on the MADRS in patients with at least mild sleep disturbance at baseline, defined by a score of ≥ 2 on Item 4;
 - Change from baseline in MADRS individual item scores at Weeks 1, 2, 3, 4, 5, and 6;

- Clinical Global Impression Scale, Bipolar version (CGI-BP):
 - Time course of improvement, measured by mean change from baseline in the CGI-BP – Severity (CGI-BP-S) score at each assessment time point, including at Week 6;
- Mean change from baseline in the Sheehan Disability Scale (SDS) total score;
- Mean change from baseline in the Quality of Life Enjoyment and Satisfaction Questionnaire – Short Form (Q-LES-Q-SF);
- Mean change from baseline in the WHO-5 Well-being Index;
- Mean change from baseline in the Neuroticism, Extraversion, and Openness to Experience-Five Factor Inventory (NEO-FFI).

Safety Secondary Objectives of Part A of this study are to determine the safety and tolerability of 2 doses of ITI-007 via changes in the following:

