The primary and key secondary efficacy endpoints will be evaluated using a gatekeeping procedure to adjust for multiplicity while controlling the overall Type I error rate in the strong sense at a two-sided alpha=0.05. The primary endpoint will serve as a gatekeeper for the key secondary endpoint in the sense that a key secondary endpoint will be tested only if at least one primary test is significant, as described in Section 7.5.4 of the protocol and detailed in the Statistical Analysis Plan (SAP).

Binary secondary endpoints (proportion of treatment responders, proportion of remitters) will be analyzed using a logistic regression model with terms for treatment and the bipolar disorder at screening (I or II) stratification variable. An estimate and 95% CI for the odds ratio between each dose of ITI-007 and placebo will be presented for each of the proportions evaluated. The CGI-BP-S, improvement in sleep, SDS, Q-LES-Q-SF, WHO-5 and NEO-FFI scores and the changes from baseline will be summarized by treatment and visit.

The analyses of secondary efficacy endpoints, other than the key secondary one, will not be adjusted for multiple comparisons.

Analysis of Secondary Effectiveness Endpoints – Part B

Analyses of effectiveness endpoints in Part B will be performed on the Safety Analysis Set and will primarily consist of change from baseline descriptive summaries of MADRS, CGI-BP-S, and Q-LES-Q-SF.

Safety Analyses – Parts A and B

All safety parameters will be summarized using the Safety Analysis Set.

Medical history, prior medications, concomitant medications, and compliance/exposure will be summarized using descriptive statistics. Safety data such as reported and observed AEs, treatment emergent AEs (TEAEs) and serious AEs (SAEs), clinical laboratory results, vital signs, physical examinations and neurological findings, ECGs, and the different rating scales will be summarized by visit (Part A and Part B) and treatment group

[figure not shown]
(Part A). Parameters planned to be collected more than once at pre-specified time points will be analyzed as an average of the measures for the relevant time point, including screening or baseline.

Reported AE terms will be coded using the latest version of the Medical Dictionary for Regulatory Activities (MeDRA). TEAEs and SAEs will be listed and summarized by system organ class (SOC), preferred term (PT), relationship to study drug, intensity (Part A and Part B) and by treatment group (Part A).

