6.2 Efficacy Assessments and Procedures

6.2.1 MADRS

The MADRS is a 10-item checklist designed to measure the overall severity of depressive symptoms. Individual items are rated by the investigator (or another ITI-approved expert site-based rater) on a scale of 0 to 6 in which a score of 6 represents the most severe symptoms for each item assessed. The total score ranges from 0 to 60.

Remission of depression based on the MADRS is generally defined as a patient with a MADRS total score of ≤ 12 at endpoint. A “responder” on the MADRS is defined as a $\geq 50\%$ reduction from baseline in total MADRS score at endpoint.

The total score on the MADRS at screening is a major criterion for inclusion in the study, as well as the primary outcome measure for the study.

In Part A, at each visit with a MADRS assessment, the rater-administered MADRS interview will be audio recorded; at each visit after the screening visit, a computer-administered MADRS interview will also be completed by patients. The computer-administered interview will involve a series of probe and follow up questions with multiple-choice response options. At all visits (except screening) the rater-administered MADRS will be conducted before the computer-administered MADRS.

In Part B, MADRS administration will be done by each patient, who will complete an interactive, computer-administered MADRS interview on the dedicated study device.

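### The sleep endpoint's population is a baseline MADRS Item 4 score of 2 or more in the synopsis objective but 4 or more in Protocol 7.1.2.2

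*Protocol*

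**What the plan says.** The Protocol Synopsis, under the other efficacy secondary objectives of Part A, assesses sleep improvement on MADRS Item 4 "in patients with at least mild sleep disturbance at baseline, defined by a score of ≥ 2 on Item 4".

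Protocol Section 7.1.2.2 lists the matching endpoint as change from baseline in the Item 4 score, for patients with a baseline score of 4 or more on that item, and words the group and the visits as "patients with mild sleep disturbance) at Weeks 1, 2, 3, 4, 5, and 6".

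Section 6.2.1 says that each MADRS item is rated "on a scale of 0 to 6 in which a score of 6 represents the most severe symptoms for each item assessed".

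The synopsis describes the analysis without repeating a cut: "The CGI-BP-S, improvement in sleep, SDS, Q-LES-Q-SF, WHO-5 and NEO-FFI scores and the changes from baseline will be summarized by treatment and visit". It also states: "The analyses of secondary efficacy endpoints, other than the key secondary one, will not be adjusted for multiple comparisons".

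Both definitions are current protocol text; neither comes from an amendment log. In the public copy, the other secondary efficacy objectives in the protocol body (Section 2.2.1) are blacked out. So is the SAP text between 3.2.1 and 3.2.3 and between 15.2 and 15.4, where this endpoint would be expected.

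**The concern.** The baseline cut decides who is analysed. The two sections use the same word, mild, for the lower limit of the group, which suggests that one population was intended. They then attach that word to two different scores. A programmer working from the synopsis and one working from Section 7.1.2.2 would build different analysis sets for the same endpoint, and each could cite the protocol.

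What is at stake is whether the reported result matches the objective. The objective concerns everyone from the mild grade upward. A result restricted to scores of 4 or more concerns a more disturbed group, and a reader who relies on the printed label would take it for the broader one.

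**Working it through.** The plan states no figure to reproduce, and no sample size, power or alpha enters. The check sets the two definitions side by side on the item scale.

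Inputs:
- Item range: 0 to 6 (Protocol 6.2.1).
- Cut in the objective: 2 or more, labelled at least mild (Protocol Synopsis).
- Cut in the endpoint definition: 4 or more, labelled mild (Protocol 7.1.2.2).

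| Baseline Item 4 score | Synopsis objective (2 or more) | Section 7.1.2.2 (4 or more) |
|---|---|---|
| 0, 1 | out | out |
| 2, 3 | **in** | **out** |
| 4, 5, 6 | in | in |

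1. The objective admits the scores {2, 3, 4, 5, 6}, and the endpoint section admits {4, 5, 6}.
2. The second set is contained in the first. The populations are nested, and they differ only in patients scoring 2 or 3.
3. Let n(k) be the number of patients with baseline score k. The number affected is n(2) + n(3), out of n(2) + n(3) + n(4) + n(5) + n(6) admitted by the objective.
4. The documents give no n(k), so only the limits can be stated. If nobody scores 2 or 3, the number affected is 0 and the cuts agree in practice. If nobody scores 4 or more, everyone admitted by the objective is affected and the group in Section 7.1.2.2 is empty. The true figure lies somewhere between.

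The labels do not settle which number was meant. Section 6.2.1 anchors only the top of the item, and nothing visible ties either 2 or 4 to a mild grade. A score of 4 is above the midpoint of the item, (0 + 6)/2 = 3, so a plain mild sits awkwardly with it. That makes a slip in the number in Section 7.1.2.2 the more natural reading. A slip in the label there cannot be excluded.

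No other visible text chooses between the cuts. The synopsis methods text names improvement in sleep with no threshold.

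**The case against.** The strongest reply accepts the inconsistency and disputes its weight. The endpoint is not a key secondary one. It lies outside the gatekeeping procedure, carries no multiplicity adjustment, and in the visible text is only summarized by treatment and visit. The next bullet of Section 7.1.2.2 also specifies change in every individual MADRS item at Weeks 1 to 6 with no baseline restriction. Item 4 change will therefore be reported with the patients scoring 2 or 3 included. All of this stands and limits the consequence. It does not remove the conflict, because the unrestricted analysis also takes in patients scoring 0 or 1 and so does not answer the objective either.

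Three stronger conclusions are tempting, and the documents do not support them.

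- A reader might infer that the sponsor was free to pick the cut after seeing the data. Protocol Section 7 says that the Part A SAP will be finalized before the interim analysis and will give further detail on endpoint definitions. SAP 5.2 has the final analyses follow the SAP, database lock, authorization of the analysis sets and unblinding. The SAP text for this endpoint is blacked out and may already fix one cut. Its absence from the public copy is not evidence that the choice was left open.
- A reader might infer that the higher cut inflates the treatment effect. Selecting high baseline scorers tends to enlarge the change within each arm through regression to the mean. The selection uses a pre-treatment score and applies to all three arms, so it does not by itself bias the comparison with placebo, which is what the objective asks about.
- A reader might want a figure for lost precision. That would need an assumed Item 4 distribution and an assumed equal standard deviation of change in the two groups. The documents supply neither, and the visible text promises no confidence interval for this endpoint.

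**Conclusion.** The point holds as an internal contradiction in the protocol. One endpoint has two baseline thresholds, 2 or more and 4 or more, on a 0 to 6 item. The groups are nested, and following Section 7.1.2.2 as written excludes patients whom the stated objective includes.

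The effect is confined to one non-key secondary endpoint. The number of patients affected is unknown, within the limits shown above. The primary analysis does not use this subgroup, so the sample size, the power and the familywise error rate are unaffected.

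The conclusion rests only on the two definitions and the item range, all of which are legible. It makes no assumption about the blacked-out SAP text. Even if the SAP states a single cut, that cut can agree with only one of the two protocol sections.

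**What to change.** Use one threshold and one matching label in the synopsis objective and in Section 7.1.2.2.

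- The simplest choice is to set Section 7.1.2.2 to a baseline Item 4 score of 2 or more, labelled at least mild, which matches the objective as written. If the more disturbed group is of interest, keep 4 or more as a separately labelled supportive subgroup.
- If 4 or more was intended, change the threshold in the objective to 4 and replace the mild wording in both places with a label that fits that score.

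Then confirm that the SAP definition of this endpoint uses the same cut, and correct it only if it does not.

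The cost is one number and possibly a label. No new data, visits or patients are needed. Protocol Section 7 allows changes to the analysis methods to be documented in the SAP without a protocol amendment. If the protocol is not otherwise being revised, a sentence in the SAP stating which cut governs, and noting the discrepancy, would be enough.

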7.1.3 Secondary Effectiveness Endpoints (Part B)

Secondary effectiveness objectives of Part B of this study are to determine whether 60 mg ITI-007, administered once daily for up to approximately 6 months to patients with bipolar disorder who have responded to treatment with ITI-007, improves and/or maintains symptoms, function, and quality of life as measured by change from baseline on the following measures:

- MADRS total score;
- CGI-BP-S;
- Q-LES-Q-SF

[REDACTED] [REDACTED]

■ [REDACTED]

■ [REDACTED]

7.1.5 Safety Endpoints (Parts A and B)

- AEs;
- YMRS total score;
- MADRS score (safety endpoint for Part B only);
- C-SSRS scores;
- AIMS scores;
- BARS scores;
- SAS score;
- Physical examination and neurological findings;
- Vital signs (blood pressure, heart rate), weight, and height (height, only at screening);
- ECGs;
- Clinical laboratory evaluations.

7.2 Sample Size Calculations

In Part A, approximately 549 patients will be randomly assigned in a 1:1:1 ratio to 1 of the 3 treatment arms, which will provide approximately 471 evaluable patients, assuming an approximate 14% early discontinuation rate before a post-dose assessment in the primary efficacy endpoint (MADRS). A sample size of 471 patients (157/arm) will provide at least 90% power to detect a clinically relevant treatment difference from placebo of 3 points on the MADRS total score within each ITI-007 dose level, with a common standard deviation of 7.5

at an overall 2-sided significance level of 0.05. It was not possible to apply the proposed Hommel procedure for multiplicity adjustments (for comparing 2 doses of ITI-007 to placebo) to the sample size calculation; therefore, the sample size calculation used a more conservative Bonferroni adjustment. The study therefore has at least 90% power to detect the previously mentioned clinically relevant treatment difference within each ITI-007 dose. The sample size calculation was performed using PASS software version 12.

In Part B, up to approximately 549 patients will be enrolled. The sample size is not based on statistical considerations, rather on the number of patients who may be eligible based on participation in Part A of the study. It is estimated that the majority of patients will continue treatment for the full 6 months.

7.3 Analysis Sets

The following analysis sets will be used in the statistical analyses.

All Patients Enrolled (ENR) Set: The ENR Set will contain all patients who signed informed consent for the study.

All Patients Randomized (RND) Set: The RND Set will contain all patients who signed the informed consent and were randomized to study drug.

Intent-to-treat (ITT) Set: The ITT Set will contain all randomly assigned patients who received at least 1 dose of study drug and who have a valid (pre-dose) baseline measurement and at least 1 valid post-baseline measurement of MADRS. Primary, secondary, and exploratory efficacy analyses of Part A data will be performed using the ITT Set. All analyses using the ITT will group patients according to randomized treatment, regardless of the treatment received during the course of the study.

Per-protocol (PP) Set: For Part A, the PP Set will contain all ITT patients who did not have any major protocol deviations. For Part B, the PP Set will contain all patients in the Safety Analysis Set who did not have any major protocol deviations. The major protocol deviation criteria will be finalized prior to any analysis. For Part A, all analyses using the PP Set will

group patients according to the treatment actually received. The classification of patients according to study drug does not apply to Part B.

Safety Analysis Set: The Safety Analysis Set will contain all patients who took at least 1 dose of study drug. All analyses using the Safety Set will group patients according to treatment actually received. In case of incorrect dosing, the treatment most often received will be taken as the actual treatment.

[REDACTED]

The following analysis sets will be used for the analyses of Part B data: ENR Set, Safety Analysis Set, and PP Sets. The classification of patients according to study drug does not apply to Part B.

Unless otherwise specified, the ITT and PP Sets will be used for analysis of efficacy endpoints in Part A and the Safety Set will be used for analysis of safety endpoints in Part A and safety and effectiveness endpoints in Part B.

7.4 Description of Subgroups to be Analyzed

Subgroup analyses of efficacy and safety variables may be conducted as deemed appropriate. For subgroup analyses using either MMRM or ANCOVA with LOCF, the corresponding subgroup terms will be added to the model: subgroup, subgroup-by-treatment, subgroup-by-visit, and subgroup-by-treatment-by-visit interactions. Subgroup analyses will be detailed in the SAP.

7.5 Statistical Analysis Methodology

Categorical variables (e.g., race and gender) will be summarized using the number and percentage of patients in specified categories will be presented. Unless otherwise specified, descriptive statistics of continuous variables (e.g., age, height, weight) will consist of the number of patients (n), mean, standard deviation, median, minimum, and maximum. Source data for summary tables and statistical analyses will be presented as patient data listings.

Unless stated otherwise, statistical tests will be 2-sided and use a 5% significance level, leading to 95% (2-sided) confidence intervals (CIs). All statistical analyses will be performed using SAS software Version 9.2 or higher. Adjustments for multiplicity due to the comparison of 2 doses of ITI-007 versus placebo for primary efficacy variables will be made using the Hommel procedure. No adjustment for multiplicity will be made for secondary efficacy (Part A) or safety variables (Part A), or any analysis of Part B data, unless otherwise stated in the SAP.

All investigative sites with fewer than 5 patients per treatment group with non-missing values of the response variable will be pooled together and considered a single site for analysis. If this results in a site still having fewer than 5 patients per treatment group, this site will be pooled together with the next smallest investigative site, if one exists; otherwise, no further pooling is needed. These pooled investigative sites will be used for any analysis that has investigative site as a fixed effect in the model. The actual investigative site numbers will be included in the listings.

Additional details regarding the statistical analysis methodology will be provided in the SAP.

7.5.1 Patient Disposition, Analysis of Demographics and Other Baseline Characteristics

Patient disposition will be summarized for each Part by treatment group, when applicable, and overall, including incidence of screen failure, and treatment or study discontinuation and the corresponding reasons. The number and percentage of randomized patients who discontinued due to an adverse event associated with worsening of bipolar depression will be

summarized. Similarly, the number and percentage of randomized patients who discontinued due to an adverse event not associated with worsening of bipolar depression will also be presented. Time to treatment discontinuation due to all reasons, adverse events, lack of efficacy, or due to any other reason of special interest will be evaluated separately using the Kaplan-Meier method, where patients who complete the On-Treatment Period or who discontinue for a reason other than the one being evaluated will be censored. The Log-rank test will be used to compare the time to discontinuation between each treatment group and the placebo group (Part A).

Demographic and baseline characteristics, including bipolar disorder diagnosis and bipolar disorder baseline efficacy measures, will be summarized for each part by treatment group for Part A only using descriptive statistics. No inferential statistics will be presented.

